- Language has been added to indicate that sites can confirm that appropriate temperature conditions have been maintained during IMP transit either by time monitoring (shipment arrival date and time) or temperature monitoring (Section 4.3.4).
- The CRF page for entry of FVIII prophylaxis treatment in the week prior to enrollment was renamed (Section 4.4, Appendix 1).
- The protocol now clarifies that a mobile nurse may administer emicizumab or perform other assessments during home visits if necessary (Sections 4.5, 4.5.5, and Appendix 1).
- Language has been added to clarify that adverse events associated with special situation that also qualify as adverse events of special interest should be reported within 24 hours (Section 5.3.5.12).
- Language regarding investigator reporting of pregnancies has been clarified (Section 5.4.3.2).
- A sentence describing a secondary efficacy endpoint was removed (Section 6.5.2.2). This sentence was inadvertently carried over from previous HAVEN study protocols but does not apply to BO41423.
- Footnote g in Appendix 1 has been clarified to state that the Emipref (patient version) and EQ-5D-5L instruments will not be completed by patients < 12 years of age.
- Footnote h in Appendix 1 has been clarified to state that the Hemophilia Joint Health Score (HJHS) assessment will be performed for patients ≥4 years of age.
- Footnote g in Appendix 2 clarifies the timing for the screening sample for anti-FVIII
 antibodies and notes that results must be available before enrollment. In addition, it
 now states that local testing will not replace the central laboratory inhibitor testing
 performed at Week 1.

Emicizumab—F. Hoffmann-La Roche Ltd 3/Protocol BO41423, Version 3

•	The scoring numbers in tables in the Comprehensive Assessment Tool of	
	Challenges in Hemophilia (CATCH) questionnaires have been removed	
	(Appendices 4–6) because there were discrepancies with the scoring manual.	The
	scoring is incorporated in the programming of the underlying algorithm.	

Substantive new information appears in italics. This amendment represents cumulative changes to the original protocol.

TABLE OF CONTENTS

PR	OTOCOL AM	ENDMENT ACCEPTANCE FORM	12
PR	OTOCOL SYI	NOPSIS	13
1.	BACKGROU	JND	21
	1.1	Background on Hemophilia A and Disease Severity	21
	1.2	Background on Emicizumab	
	1.2.1	Molecule and Preclinical Data	23
	1.2.2	Clinical Experience	24
	1.3	Study Rationale and Benefit-Risk Assessment	24
2.	OBJECTIVE	ES AND ENDPOINTS	26

Appendix 5	Comprehensive Assessment Tool of Challenges in	
	Hemophilia (CATCH): Pediatric	113
Appendix 6	Comprehensive Assessment Tool of Challenges in	
	Hemophilia (CATCH): Caregiver	121
Appendix 7	EuroQol 5-Dimension, 5-Level Questionnaire (EQ-5D-5L)	123
Appendix 8	Emicizumab Preference Survey (EmiPref): Patient	125
Appendix 9	Emicizumab Preference Survey (EmiPref): Caregiver	127
Appendix 10	Clinical Criteria for Diagnosing Anaphylaxis	129
Appendix 11	Anaphylaxis Precautions	130
Appendix 12	WHO Toxicity Grading Scale for Determining the Severity of	
	Laboratory Abnormalities and Adverse Events	131
Appendix 13	Menstrual Bleeding Questionnaire	136
Appendix 14	Menstruation Diary	141

PROTOCOL AMENDMENT ACCEPTANCE FORM

TITLE:	A MULTICENTER, OPEN-LABEL STUDY TO EVALUATE THE SAFETY, EFFICACY, PHARMACOKINETICS, AND PHARMACODYNAMICS OF EMICIZUMAB IN PATIENTS WITH MILD OR MODERATE HEMOPHILIA A WITHOUT FVIII INHIBITORS
PROTOCOL NUMBER:	BO41423
VERSION NUMBER:	3
EUDRACT NUMBER:	2019-002179-32
IND NUMBER:	122954
NCT NUMBER:	NCT04158648
TEST PRODUCT:	Emicizumab (RO5534262)
MEDICAL MONITOR:	, Ph.D.
SPONSOR:	F. Hoffmann-La Roche Ltd
I agree to conduct the stud	ly in accordance with the current protocol.
Principal Investigator's Signati	ure Date

Please retain the signed original of this form for your study files. Please return a copy of the signed form to your local study monitor.

Emicizumab—F. Hoffmann-La Roche Ltd 12/Protocol BO41423, Version 3

PROTOCOL SYNOPSIS

TITLE: A MULTICENTER, OPEN-LABEL STUDY TO EVALUATE THE

SAFETY, EFFICACY, PHARMACOKINETICS, AND

PHARMACODYNAMICS OF EMICIZUMAB IN PATIENTS WITH

MILD OR MODERATE HEMOPHILIA A WITHOUT FVIII

INHIBITORS

PROTOCOL NUMBER: BO41423

VERSION NUMBER: 3

EUDRACT NUMBER: 2019-002179-32

IND NUMBER: 122954

NCT NUMBER: NCT04158648

TEST PRODUCT: Emicizumab (RO5534262)

PHASE: Phase III

INDICATION: Mild or moderate hemophilia A

SPONSOR: F. Hoffmann-La Roche Ltd

Objectives and Endpoints

This study will evaluate the safety, efficacy, pharmacokinetics, and pharmacodynamics of emicizumab in patients of all ages with mild (factor VIII [FVIII] level between >5% and <40%) or moderate hemophilia A (FVIII level between \ge 1% and \le 5%) without inhibitors against FVIII whose bleeding phenotype warrants prophylactic treatment. Specific objectives and corresponding endpoints for the study are outlined below.

Safety Objective

The safety objective for this study is to evaluate the safety profile of emicizumab in patients with non-severe hemophilia A without inhibitors on the basis of the following endpoints:

- Incidence and severity of adverse events, with severity determined according to WHO
 Toxicity Grading Scale
- Incidence of thromboembolic events
- Incidence of thrombotic microangiopathy
- Change from baseline in physical examination findings
- Change from baseline in and vital signs
- Change from baseline in ECG parameters
- Incidence of laboratory abnormalities
- Incidence and severity of injection-site reactions
- Incidence of adverse events leading to drug discontinuation
- Incidence of severe hypersensitivity, anaphylaxis, and anaphylactoid events
- Incidence and significance of anti-emicizumab antibodies
- Incidence of de novo development of FVIII inhibitors

Emicizumab—F. Hoffmann-La Roche Ltd

13/Protocol BO41423, Version 3

Efficacy Objectives

Primary Efficacy Objective

The primary efficacy objective for this study is to evaluate the efficacy of emicizumab on the basis of the following endpoint:

Number of treated bleeds over time (i.e., bleed rate)

Secondary Efficacy Objectives

The secondary efficacy objective for this study is to evaluate the efficacy of emicizumab on the basis of the following endpoints:

- Number of all bleeds (i.e., those treated and untreated with FVIII) over time
- Number of joint bleeds over time
- Number of target joint bleeds over time (target joints are defined as joints with ≥3 bleeds occurring in the same joint during the last 24 weeks or unresolved target joints)

An unresolved target joint is defined as a target joint that does not fulfill the criterion of ≤ 2 bleeds into this joint within a consecutive 12-month period.

- Number of spontaneous bleeds over time (spontaneous bleed rate)
- Joint health, as assessed through use of the Hemophilia Joint Health Score at specified timepoints
- Health-related quality of life (HRQoL), as assessed through use of the Comprehensive Assessment Tool of Challenges in Hemophilia (CATCH) Questionnaire over time
- Preference for emicizumab compared with previous FVIII regimen, as assessed through use of the Emicizumab Preference Survey (EmiPref) at Week 17
- Effect of emicizumab prophylaxis treatment on physical activity compared with physical activity at baseline
- Effect of emicizumab prophylaxis treatment on menstruation heaviness and menstruationrelated quality of life in female patients, as assessed through the use of the Menstrual Bleeding Questionnaire (MBQ) and the Menstruation Diary (MD) with the Pictorial Blood Assessment Chart (PBAC)

Pharmacokinetic Objective

The pharmacokinetic (PK) objective for this study is to characterize the emicizumab PK profile on the basis of the following endpoint:

Plasma concentration of emicizumab at specified timepoints

Immunogenicity Objective

The immunogenicity objective for this study is to evaluate the immune response to emicizumab on the basis of the following endpoint:

- Prevalence of anti-drug antibodies (ADAs) at baseline and incidence of ADAs during the study
- Number and proportion of patients who develop anti-FVIII inhibitors (titer≥ 0.6 BU/mL) at specified timepoints

Biomarker Objective

The exploratory biomarker objective for this study is to investigate the effect of emicizumab on pharmacodynamic (PD) parameters, including but not limited to thrombin generation, FVIII activity, FVIII protein, D-dimer, and prothrombin fragment 1+2 (PF1+2) at regular intervals throughout the study and at times of treated bleeds. Changes over time in biomarkers related to bone and joint health may also be explored.

Health Status Utility Objective

The exploratory health status utility objective for this study is to evaluate health status utility scores of patients treated with emicizumab on the basis of the following endpoint:

Emicizumab—F. Hoffmann-La Roche Ltd

14/Protocol BO41423, Version 3

 Change from baseline in EuroQol 5-Dimension 5-level Questionnaire (EQ-5D-5L) index utility and visual analog scale scores at specified timepoints

Study Design

Description of Study

Study BO41423 is a multicenter, open-label, single-arm study designed to evaluate the safety, efficacy, pharmacokinetics, and pharmacodynamics of emicizumab in patients with mild or moderate hemophilia A without inhibitors against FVIII. Four loading doses of emicizumab 3 mg/kg will be administered subcutaneously once a week (QW) for 4 weeks followed by patient preference of one of the following maintenance regimens: 1.5 mg/kg QW, 3 mg/kg every 2 weeks (Q2W), or 6 mg/kg every 4 weeks (Q4W). The three maintenance dose regimens have shown equivalent average steady-state exposure, and demonstrated consistent efficacy and safety, and are approved in several countries for the treatment of Hemophilia A with or without FVIII inhibitors. As patients with mild or moderate Hemophilia A have residual FVIII levels of ≥1%, it is of interest to collect safety data over a longer time period. Therefore, in this study, the observation time to primary analyses was extended to approximately 52 weeks compared with prior Phase III studies investigating emicizumab.

Patients (or their legally authorized representative herein referred to as patient[s]) will choose the preferred emicizumab maintenance regimen (1.5 mg/kg SC QW, 3 mg/kg SC Q2W, or 6 mg/kg SC Q4W) after consultation with his or her treating physician. The chosen regimen needs to be maintained throughout the study until completion of at least 52 weeks.

During the study, individual bleeds will be captured by the patient as the bleeds occur using a Bleed and Medication Questionnaire. Breakthrough bleeds will be treated with FVIII at the lowest dose expected to achieve hemostasis.

Female patients of childbearing potential will be administered two specific patient-reported outcome measures related to their menstruation (both questionnaires administered on paper): the MBQ will assess the menstrual bleed-related heaviness, pain, irregularity and quality of life; the Menstruation Diary (MD) with the PBAC will assess the use of sanitary products for menstruation (including the number of products used, the amount of bleeding, the occurrence and size of clots, and the number of episodes of heavy bleeding (flooding)).

HRQoL (CATCH and EmiPref) and health status (EQ-5D-5L) will be assessed as outlined in the schedule of activities. These measures will be captured either on paper questionnaires or on a site-based tablet available to patients during clinic visits.

Safety assessments will include physical examinations, vital signs, ECG, laboratory assessments (serum chemistry and hematology including complete blood count with differential), anti-drug antibodies (ADAs), and FVIII inhibitors. Adverse events will be captured on an ongoing basis, as they occur during the study.

Exploratory PD biomarkers (e.g., FVIII activity, thrombin generation) will be collected on a regular basis throughout the study and will be coupled with a PK assessment for days where PK and PD samples will be drawn.

Biomarkers related to thromboembolism (e.g., D-dimer, PF1+2) and immunologic biomarkers (i.e., anti-emicizumab antibodies) will be measured on a regular basis throughout the study. Exploratory PD biomarkers and safety biomarkers will be collected within 24 hours but no later than 48 hours of a treated bleed.

After 24 weeks on prophylactic emicizumab, patients with suboptimal bleed control will be offered the option to increase their dose to 3 mg/kg QW, with approval from the Medical Monitor, if the protocol-defined criteria of suboptimal response is met.

Interim data reviews may be performed at various timepoints (e.g., for regulatory submissions), and the primary analysis for all patients will be conducted after 50 patients with moderate hemophilia A have completed 52 weeks of emicizumab treatment, are lost to follow-up, or have withdrawn, whichever occurs first. The primary analysis will occur at the specified time regardless if no patients with mild hemophilia A are enrolled; however, enrollment will be left open for patients with mild hemophilia A in order to enroll approximately 20 such patients. The total number of patients in the study might slightly exceed 70 patients depending on the number of female patients enrolled. Ideally, at least 5 female patients will be enrolled. If these are not

Emicizumab—F. Hoffmann-La Roche Ltd 15/Protocol BO41423, Version 3

recruited within the pool of 70 patients, the enrollment will remain open until they are enrolled or until the cutoff date of primary analysis, whichever occurs sooner. Note that all patients will be included in the primary analysis irrespective of their follow-up time. After the primary analysis, patients will continue to receive emicizumab according to the Roche Policy on post study drug access until emicizumab is approved and accessible to patients commercially.

Patients who discontinue study drug prior to end of study will return to the clinic for a safety follow-up visit 24 weeks after the last dose of study drug. Patients who complete or discontinue from the study will return to the clinic for a study completion/discontinuation visit.

Number of Patients

Approximately 70 patients of all age groups will be enrolled in the study consisting of approximately 20 patients with mild and approximately 50 patients with moderate hemophilia A without FVIII inhibitors whose phenotype warrants prophylaxis. The total number of patients in the study might slightly exceed 70 patients depending on the number of female patients enrolled.

Target Population

Inclusion Criteria

Patients must meet the following criteria for study entry:

- Signed Informed Consent Form (signed by patient's legally authorized representative for patients who have not attained the age of majority)
- Signed Assent Form when appropriate, as determined by patient's age and individual site and country standards
- Willingness and ability to comply with schedules visits, treatment plans, laboratory tests and other study procedures
- Diagnosis of mild (FVIII level between >5% and <40%) or moderate (FVIII level between ≥1% and ≤5%) congenital Hemophilia A without FVIII inhibitors
- Weight ≥3 kg
- Need for prophylaxis based on investigator assessment
- A negative test for inhibitor (i.e., < 0.6 BU/mL) within 8 weeks prior to enrollment
- No documented inhibitor (i.e., <0.6 BU/mL), FVIII half-life <6 hours, or FVIII recovery <66% in the last 5 years

Patients who completed successful immune tolerance induction (ITI) at least 5 years before screening are eligible, provided they have had no evidence of inhibitor recurrence (permanent or temporary) as may be indicated by a detection of an inhibitor, FVIII half-life < 6 hours or FVIII recovery < 66% since completing ITI.

- Documentation of the details of prophylactic or episodic FVIII treatment and of number of bleeding episodes for at least the last 24 weeks prior to enrollment
- Adequate hematologic function, defined as platelet count \geq 100,000 cells/ μ L and hemoglobin \geq 8 g/dL (4.97 mmol/L) at the time of screening
- Adequate hepatic function defined as total bilirubin ≤1.5×age-adapted upper limit of normal (ULN) (excluding Gilbert syndrome) and both AST and ALT ≤3×age-adapted ULN at the time of screening, and no clinical signs or known laboratory/radiographic evidence consistent with cirrhosis
- Adequate renal function, defined as serum creatinine ≤2.5 x age-adapted ULN and creatinine clearance ≥30 mL/min by Cockroft-Gault formula
- For women of childbearing potential: agreement to remain abstinent (refrain from heterosexual intercourse) or use contraception as defined below:

Women must remain abstinent or use contraceptive methods that result in a failure rate of <1% per year during the treatment period and for at least 24 weeks after the final dose of study drug.

Emicizumab—F. Hoffmann-La Roche Ltd 16/Protocol BO41423, Version 3

A woman is considered to be of childbearing potential if she is postmenarcheal, has not reached a postmenopausal state (≥ 12 continuous months of amenorrhea with no identified cause other than menopause), and is not permanently infertile due to surgery (i.e., removal of ovaries, fallopian tubes, and/or uterus) or another cause as determined by the investigator (e.g., Müllerian agenesis). The definition of childbearing potential may be adapted for alignment with local guidelines or regulations.

Examples of contraceptive methods with a failure rate of <1% per year include bilateral tubal ligation, male sterilization, hormonal contraceptives that inhibit ovulation, hormone-releasing intrauterine devices, and copper intrauterine devices.

The reliability of sexual abstinence should be evaluated in relation to the duration of the clinical trial and the preferred and usual lifestyle of the patient. Periodic abstinence (e.g., calendar, ovulation, symptothermal, or postovulation methods) and withdrawal are not acceptable methods of contraception. If required per local guidelines or regulations, locally recognized acceptable methods of contraception and information about the reliability of abstinence will be described in the local Informed Consent Form.

Exclusion Criteria

Patients who meet any of the following criteria will be excluded from study entry:

- Inherited or acquired bleeding disorder other than mild (FVIII level between >5% and <40%) or moderate (FVIII level between ≥1% and ≤5%) congenital hemophilia A
- History of illicit drug or alcohol abuse within 48 weeks prior to screening, in the investigator's judgment
- Previous (within the last 12 months) or current treatment for thromboembolic disease (with the exception of previous catheter-associated thrombosis for which anti-thrombotic treatment is not currently ongoing) or signs of thromboembolic disease
- Other conditions (e.g., certain autoimmune diseases) that may currently increase the risk of bleeding or thrombosis
- History of clinically significant hypersensitivity associated with monoclonal antibody therapies or components of the emicizumab injection
- Planned surgery during the emicizumab loading dose phase
 Surgeries in patients on emicizumab from Week 5 onwards are allowed.
- Known HIV infection with CD4 counts < 200 cells/μL
- Concomitant disease, condition, significant abnormality on screening evaluation or laboratory tests, or treatment that could interfere with the conduct of the study, or that would in the opinion of the investigator, pose an additional unacceptable risk in administering study drug to the patient
- Receipt of any of the following:
 - An investigational drug to treat or reduce the risk of hemophilic bleeds within 5 half-lives of last drug administration with the exception of prior emicizumab prophylaxis (prior investigational or commercial emicizumab use is not an exclusion criterion)
 - A non-hemophilia-related investigational drug within last 30 days or 5 half-lives, whichever is shorter
 - Any other investigational drug currently being administered or planned to be administered
- Inability to comply with the study protocol in the opinion of the investigator
- Pregnant or breastfeeding, or intending to become pregnant during the study

Women of childbearing potential must have a negative serum pregnancy test result within 7 days prior to initiation of study drug.

Emicizumab—F. Hoffmann-La Roche Ltd 17/Protocol BO41423, Version 3

End of Study

The end of this study is defined as the date when the last remaining patient has completed the last visit, as defined by the following criteria: completion of at least 52 weeks of emicizumab treatment during the study and either transfers to commercially available emicizumab or receives further emicizumab per Roche Global Policy on Continued Access to Investigational Medicinal Products OR completion of the end of study safety follow-up visit 24 weeks after discontinuing emicizumab OR withdrawal of consent OR lost to follow-up.

Length of Study

The total length of the study, from screening of the first patient to the end of the study, is expected to be approximately 27 months.

Investigational Medicinal Products

Test Product (Investigational Drug)

The investigational medicinal product for this study is emicizumab. The emicizumab dosing regimen to be tested is emicizumab 3 mg/kg SC QW for 4 weeks followed by a maintenance dose of either 1.5 mg/kg SC QW, 3 mg/kg SC Q2W, or 6 mg/kg SC Q4W.

All patients with suboptimal control of bleeding as defined by the protocol will be offered the option to increase their emicizumab maintenance dose to 3 mg/kg QW, with approval from the Medical Monitor. Suboptimal response is defined as follows: ≥2 qualifying bleeds within 24 weeks while on prophylactic emicizumab.

Statistical Methods

Primary Analysis

The primary analysis will be performed after 50 patients with moderate hemophilia A have either completed 52 weeks of emicizumab treatment, are lost to follow-up, or have withdrawn prematurely, whichever occurs first. Data from all patients (including any female patients and any patients with mild hemophilia A) will be included in the primary analysis.

The safety analyses population will be based on all patients who received at least one administration of emicizumab. Safety will be assessed through descriptive summaries of adverse events, laboratory test results (serum chemistry and hematology including complete blood count with differential and platelet counts), ECGs, vital signs, ADAs, and de novo FVIII inhibitors. To evaluate the overall safety of emicizumab, the incidence of adverse events will be summarized and presented by System Organ Class mapped term, appropriate thesaurus level, and toxicity grade. For clinical laboratory data, summary statistics will be presented. In addition, shift tables describing changes from baseline will be presented using the WHO Toxicity Grading Scale.

Summaries will be presented overall, by dosing regimen, and, if applicable, by disease severity. Further details will be provided in the Statistical Analysis Plan.

The key efficacy objective is to characterize the efficacy of emicizumab based on the number of treated bleeds over time. The clinical effect of prophylactic emicizumab will be assessed via the annualized bleed rate estimated using a negative binomial regression model, which accounts for different follow-up times, with the number of bleeds from patients as a function of the time such that each patient who stays in the study is included as an offset in the model. A detailed description of the statistical methods and the summaries, if applicable, presented by dosing regimen and/or by disease severity for the efficacy analyses will be provided in the Statistical Analysis Plan.

Determination of Sample Size

The overall sample size of approximately 70 patients (approximately 50 patients with moderate disease, approximately 20 patients with mild disease) is based primarily on clinical considerations, taking into account the limited number of patients with non-severe hemophilia A. This sample size is expected to provide statistically robust point estimates with meaningfully narrow CIs in the overall group of enrolled patients, assuming the same efficacy across dosing regimens.

Optional Interim Analyses Reviews

Interim data reviews may be performed at various timepoints for regulatory submissions.

Emicizumab—F. Hoffmann-La Roche Ltd

18/Protocol BO41423, Version 3

LIST OF ABBREVIATIONS AND DEFINITIONS OF TERMS

Abbreviation	Definition
ABR	annualized bleed rate
ADA	anti-drug antibody
aPCC	activated prothrombin complex concentrate
BMQ	Bleed and Medication Questionnaire
CATCH	Comprehensive Assessment Tool of Challenges in Hemophilia
DSC	daily step count
EC	Ethics Committee
eCRF	electronic Case Report Form
EDC	electronic data capture
EmiPref	Emicizumab Preference Survey
EQ-5D-5L	European Quality of Life 5-Dimension, 5-Level Questionnaire
FDA	Food and Drug Administration
FIXa	activated factor IX
FVIII	factor VIII
FX	factor X
HCP	healthcare provider
HIPAA	Health Insurance Portability and Accountability Act
HJHS	Hemophilia Joint Health Score
HRQoL	health-related quality of life
ICH	International Council for Harmonisation
IMP	investigational medicinal product
IND	Investigational New Drug (application)
IRB	Institutional Review Board
ITI	immune tolerance induction
IxRS	interactive voice or web-based response system
MBQ	Menstrual Bleeding Questionnaire
MD	Menstruation Diary
MN	mobile nursing
MVPA	moderate to vigorous physical activity
PBAC	Pictorial Blood Assessment Chart
PD	pharmacodynamic
PF1+2	prothrombin fragment 1+2
PK	pharmacokinetic
PRO	patient-reported outcome
Q2W	every 2 weeks
Q4W	every 4 weeks

Emicizumab—F. Hoffmann-La Roche Ltd

19/Protocol BO41423, Version 3

Abbreviation	Definition
QW	once a week
RBR	Research Biosample Repository
rFVIIa	recombinant activated factor VII
SAP	Statistical Analysis Plan
TMA	thrombotic microangiopathy
ULN	upper limit of normal
VAS	visual analog scale
WES	whole exome sequencing
WGS	whole genome sequencing

1. BACKGROUND

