The EQ-5D-5L is a validated, self-report, health status questionnaire that is used to calculate a health status utility score for use in health economic analyses (EuroQol Group 1990; Brooks 1996; Herdman et al. 2011; Janssen et al. 2013) (see Appendix 7). There are two components to the EQ-5D-5L: a five-item health state profile that assesses mobility, self-care, usual activities, pain/discomfort, and anxiety/depression, as well as a VAS that measures health state. Published weighting systems allow for creation of a single composite score of the patient's health status. The EQ-5D-5L takes approximately 3 minutes to complete and will be completed by patients 12 years of age and older. It will be used in this study for informing pharmacoeconomic evaluations.

Emicizumab Preference Survey

Patient preference will be assessed through the EmiPref (see Appendix 8 and Appendix 9). Patients and/or caregivers will be asked to report which treatment regimen they would prefer to continue to receive or administer after having been treated with or administered IV FVIII prior to study entry and SC emicizumab during the study. Patients and/or caregivers who express a preference will then be asked to identify which reasons may have influenced their decision and indicate the top three reasons for this choice. This assessment will be performed at Week 17 when patients have gained sufficient experience with SC injection of emicizumab, while still reliably recalling their experience with prior therapy.

Menstrual Bleeding Questionnaire and Menstruation Diary

For females with bleeding disorders, menorrhagia can further diminish their health-related quality of life (Shankar et al. 2008). Menorrhagia is defined subjectively as excessive or prolonged loss of blood on a regular cyclical basis or objectively as menstrual blood loss≥80 mL for the whole period (Higham et al. 1990).

All female patients of childbearing potential will be asked to complete two PROs, the MBQ and MD (See Appendix 13 and Appendix 14).

- The MBQ is a validated measure for menorrhagia and is widely used in research and clinical practice to assess impact on the menstrual bleed-related heaviness, pain, irregularity, and quality of life (Matteson et al. 2015). The MBQ is a 20-item measure covering four aspects regarding heavy menstrual bleeding: heaviness (8 items), quality of life (8 items), irregularity (1 item), and pain (1 item).

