(see Appendix 1) and have the option to correct or complete these in agreement with the patient via a Data Request Form process or via a web-based portal, once implemented.

The Sponsor will have view-access only but will perform a review of the bleed and bleed medication data as per the Medical Data Review Plan and have the option to correct or complete these in agreement with the patient via a Data Request Form process or via a web-based portal, once implemented.

Reporting of Menstrual Bleed and Menstruation Diary Data

All female patients of childbearing potential will be asked to complete the following paper questionnaire and diary:

- MBQ in the clinic on Day 1 and subsequently every 4 weeks to document the menstrual bleed-related heaviness, pain, irregularity, and quality of life during the past month (See Appendix 13).
- MD with the PBAC to document at home the use of menstrual products during the
 past month (including the number of products used, the amount of bleeding, the
 occurrence and size of clots, and the number of episodes of heavy bleeding
 (flooding)). The MD with PBAC will be given to patients on Day 1 and should be
 completed monthly on days of menstruation (See Appendix 14). The patient should
 return the completed MD with PBAC to the site personnel during the next clinic visit.

All MBQ and MD data will be entered into the study database by site personnel.

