3.3.2.4 Menstruation Heaviness and Menstruation-related Quality of Life

MBQ will be summarized descriptively over time, including change from baseline for individual subscales (heaviness, quality of life, irregularity, and pain) and total score. Pictorial Blood Assessment Chart (PBAC) scores will be summarized descriptively over time. If the number of female patients of childbearing potential is too low to provide reliable summaries, the data will be listed and presented in individual patient plots where applicable.

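### Eligibility for the menstrual questionnaires rests on a contraception definition that can leave out a few women who still menstruate; define it by menstruation instead

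*Protocol*

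**What the plan says.** Menstruation heaviness and menstruation-related quality of life form a secondary efficacy objective. It is measured with the Menstrual Bleeding Questionnaire (MBQ) and the Menstruation Diary (MD) with the Pictorial Blood Assessment Chart (PBAC).

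- **Who receives them.** The synopsis design text says "Female patients of childbearing potential will be administered two specific patient-reported outcome measures related to their menstruation". Protocol 4.5.7.2 says "All female patients of childbearing potential will be asked to complete two PROs, the MBQ and MD" and 4.5.7.4 says "All female patients of childbearing potential will be asked to complete the following paper questionnaire and diary". Appendix 1 footnote u applies the same restriction, and applies it also to the menstruation start and end dates entered on the eCRF.
- **What the term means.** The definition sits under the contraception criterion (synopsis and Protocol 4.1.1). A woman qualifies if she is past menarche, not postmenopausal, and "is not permanently infertile due to surgery (i.e., removal of ovaries, fallopian tubes, and/or uterus") or by another cause that the investigator determines. It adds: "The definition of childbearing potential may be adapted for alignment with local guidelines or regulations".
- **Tubal ligation.** Protocol 4.5.5 and Appendix 1 footnote q count women with a tubal ligation as being of childbearing potential.
- **The objective.** The synopsis objective refers to "quality of life in female patients, as assessed through the use of the Menstrual Bleeding Questionnaire (MBQ") with no such restriction. Protocol 2.2.2 and SAP 2.3.2 include it.
- **Numbers.** "Ideally, at least 5 female patients will be enrolled" (synopsis, Protocol 3.1 and 3.3.2). Enrolment can stay open to reach this number.
- **Analysis.** Summaries are descriptive. SAP 3.3.2.4 provides a fallback that begins "If the number of female patients of childbearing potential is too low to provide reliable summaries": the data are then listed and shown in individual patient plots.

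**The concern.** Childbearing potential is the right concept for contraception and pregnancy testing. The menstrual endpoint needs a different one: whether the woman can menstruate. Where the two part, a woman can have the outcome of interest and be given neither instrument. Because the definition may also be adapted to local rules, the measured group could differ between countries for reasons that have nothing to do with menstrual bleeding.

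The MBQ and the MD with PBAC are the only instruments named for this objective, so a woman outside the definition contributes nothing to it after baseline. The trial hopes for at least five females and may hold enrolment open to find them. In a group that small, each menstruating woman counts.

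**Working it through.** The plan gives no precision or sample-size figure for the menstrual endpoint, so there is none to reproduce. The check has two parts.

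**1. Does the definition match menstruation?** Taking the definition clause by clause:

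| Status | Of childbearing potential? | Can menstruate? |
|---|---|---|
| Before menarche | No | No |
| Postmenopausal (12 months or more of amenorrhea) | No | No |
| Uterus removed, both ovaries removed, or Müllerian agenesis | No | No |
| Amenorrhea under 12 months | Yes | Yes, possibly |
| Tubal ligation | Yes | Yes |
| Fallopian tubes removed, uterus and ovaries intact | **No** | **Yes** |
| Other permanent infertility, uterus and ovarian function intact | **No** | **Yes** |

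The rule agrees with menstrual status in every row but the last two. In the list of surgical causes, the and/or wording makes removal of the tubes sufficient alone. A woman with ligated tubes is therefore measured, while a woman with removed tubes and the same menstrual bleeding is not.

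**2. How large could the loss be?** Inputs:

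- n = 5 female patients, the hoped-for minimum in Protocol 3.1.
- p = share of enrolled female patients who menstruate but fall outside the definition. The documents do not give it, so p is assumed and shown as a range.

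Formulas: expected loss = n × p; chance of losing at least one = 1 − (1 − p)^n.

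| Assumed p | Expected loss, n = 5 | Chance of at least one lost, n = 5 | Same, n = 10 |
|---|---|---|---|
| 1% | 5 × 0.01 = 0.05 | 1 − 0.99^5 = 4.9% | 9.6% |
| 2% | 0.10 | 1 − 0.98^5 = 9.6% | 18.3% |
| 5% | 0.25 | 1 − 0.95^5 = 22.6% | 40.1% |
| 10% | 0.50 | 1 − 0.90^5 = 41.0% | 65.1% |

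With n = 5, the probability of losing exactly one relative to losing none is 5p / (1 − p). This is below 1 whenever p is below 1/6, so the likeliest loss is zero at every p in the table.

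If all five women menstruated, one loss would remove 1/5 = 20% of the follow-up data. The five counts females of any age, so the number who menstruate may be smaller and the share per woman larger. Enrolment may also exceed five, which makes the share smaller.

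**The case against.** The strongest reply is that this is a rare case with little consequence, and much of that stands.

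- A reader might infer that the definition excludes menstruating women in general. It does not: it covers nearly all of them, and women with a tubal ligation are expressly kept in.
- A reader might infer that an excluded woman is never asked about menstrual bleeding. Protocol 4.5.2 records menstruation and menorrhagia history at baseline for female patients without the restriction, and Protocol 6.3 summarises menstruation history for them. What she misses is follow-up on the endpoint.
- A reader might infer that patients will be lost. The documents give no frequency. The percentages above are illustrations and do not forecast a loss.
- A reader might infer that a lost woman would tip the analysis into listings. SAP 3.3.2.4 sets no numerical threshold, and with so few women the fallback may apply anyway. SAP 3 and 3.3 exclude formal hypothesis testing, so neither power nor error rates are at stake.
- The difference between the synopsis objective and Protocol 2.2.2 can be read as abbreviation, since the synopsis design text restricts the questionnaires in the same way as the body. Collection and analysis are consistent with each other.
- No actual local adaptation is identified, and one could widen the group as well as narrow it.

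What the reply does not remove is the mismatch in the last two rows of the first table. The population for an efficacy endpoint is chosen by a criterion written for another purpose. Choosing it by menstrual status can add data from women now left out, and the baseline history already identifies them.

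**Conclusion.** The point holds as a minor one. The MBQ and MD with PBAC population is set by a contraception definition that closely but not fully tracks menstruation and may be adapted locally. A menstruating woman without fallopian tubes, or permanently infertile for another cause, can be left out and would then have a baseline history but no follow-up on the endpoint.

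The likely size is small. With five women, the chance of losing at least one runs from 4.9% to 41.0% as the assumed share goes from 1% to 10%, and the expected loss stays at half a patient or less. These figures rest on an assumed share and on exactly five females enrolled; the protocol gives five only as an ideal minimum. The consequence is possible missing descriptive data on one secondary objective. The conclusions on bleed rate and safety are untouched.

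**What to change.** At the next amendment, for the MBQ, the MD with PBAC and the accompanying menstruation dates only, define the population as all female patients who are postmenarcheal, not postmenopausal and have a uterus. State that women with temporary amenorrhea are included, and that the rule applies regardless of childbearing potential or any local adaptation of that term. The MBQ already opens by asking about any bleeding in the past month and routes a negative answer to question 12, so months without bleeding need no new handling.

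Use the same wording in:

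- the synopsis objective and design text;
- Protocol 2.2.2, 3.1, 3.3.6, 4.5.7.1, 4.5.7.2, 4.5.7.4 and 6.5.2.2, and Appendix 1 footnote u;
- SAP 2.3.2 and 3.3.2.4, and the matching footnote in SAP Appendix 2.

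Leave the childbearing-potential definition as it is for contraception and pregnancy testing.

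The cost is wording edits in several places, which go through the usual approval under Protocol 9.6, and paper forms for at most a few more women. No visits are added.
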